1 INTRODUCTION

1.1 Hemophilia A

Hemophilia A is an inherited sex-linked disorder of blood coagulation in which affected males do not produce functional coagulation factor VIII (FVIII) in sufficient quantities to achieve satisfactory hemostasis. The incidence of congenital hemophilia A is approximately 1 in 10,000 births. Disease severity is classified according to the level of FVIII activity (% of normal) as mild (>5% to <40%), moderate (1% to 5%), or severe (<1%).

The deficiency in FVIII predisposes patients with hemophilia A to recurrent bleeding episodes (BEs) in joints, muscles, or internal organs, either spontaneously or as a result of accidental or surgical trauma. Without adequate treatment, these repeated hemarthroses and hematomas lead to long-term sequelae with severe disability. Less frequent but more severe bleeding sites are the central nervous system, the urinary or gastrointestinal tract, the eyes, and the retroperitoneum.

Patients with hemophilia A are at high risk of developing major and life-threatening BEs after surgical procedures, even after minor interventions such as tooth extraction. Replacement therapy with exogenous FVIII, either plasma-derived or recombinant, successfully adjusts hemostasis in these patients in a temporary manner.

1.2 Wilate

Wilate is a plasma-derived, stable, highly purified, double virus inactivated concentrate of freeze-dried active von Willebrand factor (VWF) and factor VIII (FVIII) prepared from cryoprecipitate and intended for the treatment of patients with von Willebrand disease (VWD) and/or hemophilia A. By introducing new biotechnological methods and optimized chromatographic media into the *Wilate* manufacturing process, it has been possible to manufacture a preparation containing the FVIII/VWF complex in its native form and almost devoid of lower molecular weight proteins.

Overall, 14 prospective clinical studies with *Wilate* have been completed, 8 in patients with VWD and 6 in patients with hemophilia A. The 6 clinical studies with *Wilate* in patients with hemophilia A were open, non-controlled studies investigating the efficacy and safety of the product in the prevention and treatment of BEs as well as in surgical prophylaxis in a total of 109 individual patients with severe hemophilia A. Of these, 81 were previously treated patients (PTPs) and 28 were previously untreated patients (PUPs).

Five of the 6 studies investigated the efficacy of *Wilate* both in the prevention and treatment of BEs and in surgical prophylaxis, and 1 study assessed the efficacy of *Wilate* in surgical prophylaxis only.

Wilate received its first market authorization in Germany in February 2005 and is currently licensed in 62 countries worldwide. In Europe, *Wilate* is approved for the treatment of both VWD and hemophilia A. In the USA, it is approved for the treatment of VWD only. This study is done to obtain approval of *Wilate* for the treatment of hemophilia A in the USA.

A summary of findings from nonclinical and clinical studies with *Wilate* is provided in the Investigator's Brochure.

1.3 Rationale for Conducting the Study

The purpose of this study is to obtain additional data on the safety and efficacy of *Wilate* in PTPs with hemophilia A with at least 150 previous exposure days (EDs) to a FVIII concentrate who undergo prophylactic treatment with *Wilate* for 6 months and a least 50 EDs, thus supplementing the existing database to obtain approval of *Wilate* for the indication hemophilia A in the USA.

1.4 Dose Rationale

The dose used for PK assessment, i.e., 50 ± 5 IU/kg, is in line with the current recommendations of the Guideline on the clinical investigation of recombinant and human plasma-derived factor VIII products (EMA/CHPM/BPWP/144533/20009), which recommends a dose of 25–50 IU/kg. It is expected that this dose will result in measurable FVIII:C plasma concentrations after 48 hours in most, if not all, patients.

The ± 5 IU/kg range (rather than a fixed dose) was included to allow the entire contents of reconstituted vials to be injected rather than taking out an exact volume, which is difficult technically and might result in dosing errors.

The doses for prophylaxis (20–40 IU/kg *Wilate*/kg BW given at intervals of 2 to 3 days), the treatment of BEs and perioperative prophylaxis (see **Section 5.4**), are as indicated in the European Summary of Product Characteristics.

1.5 Benefit-Risk Statement

The following adverse reactions are known to occur with other VWF/FVIII preparations and may also occur with the use of *Wilate*:

- Hypersensitivity or allergic reactions (which may include angioedema, burning, and stinging at the infusion site, chills, flushing, generalized urticaria, headache, hives, hypotension, lethargy, nausea, restlessness, tachycardia, tightness of the chest, tingling, vomiting, wheezing) have been observed upon use of *Wilate* and may, in some cases, progress to severe anaphylaxis (including shock) with or without fever. In rare occasions, fever has been observed.

- The formation of neutralizing antibodies (inhibitors) to FVIII is a known complication in the management of hemophilia A. These inhibitors are usually IgG immunoglobulins directed against the FVIII procoagulant activity, which are quantified in Bethesda Units (BU) per mL of plasma. As preventive measure, hemophilia A patients should not be switched thoughtlessly from one FVIII concentrate to another. Patients should be carefully monitored for the development of inhibitors by appropriate clinical observations and laboratory tests.
- As for all medicinal products prepared from human blood or plasma, infectious diseases due to transmission of infective agents cannot be totally excluded. This applies also to pathogens of hitherto unknown origin. The manufacturing process of *Wilate*, which includes 2 viral inactivation steps with different chemical/physical action principles represents a high standard for plasma-derived concentrates in terms of pathogen safety. The measures taken are considered effective for enveloped viruses such as human immunodeficiency virus (HIV), hepatitis B virus (HBV) and hepatitis C virus (HCV), and for the non-enveloped hepatitis A virus. The measures taken may be of limited value against non-enveloped viruses such as parvovirus B19.

In view of its state-of-the-art manufacturing process and available clinical and postmarketing evidence, the benefit-risk evaluation of *Wilate* is positive.

2 STUDY OBJECTIVES

2.1 Primary Objective

The primary objective of this study is to determine the efficacy of *Wilate* in the prophylactic treatment of previously treated patients (PTP) with severe hemophilia A.

2.2 Secondary Objectives

The secondary objectives of this study are to:

- Determine the efficacy of *Wilate* in the treatment of breakthrough bleeding episodes (BEs)
- Calculate the FVIII:C pharmacokinetics (PK) for *Wilate* at baseline and after 6 months of prophylactic treatment
- Calculate the FVIII:C incremental IVR of *Wilate* over time (at baseline, and at 3 and 6 months of treatment)
- Assess the association between ABO blood type and the FVIII:C half-life of *Wilate*
- Assess the association between the VWF:Ag concentration and the FVIII:C half-life of *Wilate*
- Assess the safety and tolerability of *Wilate*
- Assess the immunogenicity of *Wilate*

2.3 Additional Objective

An additional objective of this study is the descriptive efficacy of *Wilate* in surgical prophylaxis.

3 INVESTIGATIONAL PLAN

3.1 Study Endpoints

3.1.1 Primary Endpoint

The primary endpoint of this study is a 50% reduction of the total annualized bleeding rate (TABR) observed in the GENA-01 study, with a total of 58.1 BEs per patient per year.

TABR will be calculated as the total number of BEs in the time period between first dose of IMP and the Study Completion Visit, divided by the duration (in years) between first dose of IMP and the Study Completion Visit. Surgery periods, and BEs occurring within these periods, will be excluded from the calculation of TABR.

3.1.2 Secondary Endpoints

The secondary endpoints of this study are the:

1. Spontaneous annualized bleeding rate (SABR), calculated in analogy with TABR
2. Efficacy of *Wilate* in the treatment of breakthrough BEs based on the proportion of BEs successfully treated with *Wilate*
3. *Wilate* consumption data (FVIII IU/kg per week per patient) for prophylaxis
4. Baseline PK parameters for FVIII:C using both the chromogenic (CHR) and one-stage (OS) assays and actual IMP potencies:
 - Area under the curve (AUC) and AUC normalized for the administered dose (AUC_{norm})
 - In vivo half-life ($T_{1/2}$)
 - Maximum plasma concentration (C_{max})
 - Time to reach maximum plasma concentration (T_{max})
 - Mean residence time (MRT)
 - Volume of distribution (Vd)
 - Clearance (CL)
 - Incremental in vivo recovery (IVR)
5. Incremental IVR of *Wilate* over time (at baseline, and at 3 and 6 months of treatment)
6. Association between AB0 blood type and the FVIII:C half-life of *Wilate*
7. Association between VWF:Ag concentration and the FVIII:C half-life of *Wilate*
8. Safety and tolerability of *Wilate* by monitoring adverse events (AEs) throughout the study
9. Immunogenicity of *Wilate* by testing for FVIII inhibitors
10. Virus safety in terms of parvovirus B19

3.1.3 Exploratory Endpoint

An exploratory endpoint of this study is the descriptive efficacy of *Wilate* in surgical prophylaxis.

3.2 Overall Study Design and Plan

This is a prospective, international, multi-center phase 3 study investigating the FVIII:C pharmacokinetics, efficacy, safety, and immunogenicity of *Wilate* in PTPs with severe hemophilia A.

Overall, 55 male patients with severe hemophilia A (<1% FVIII:C) aged ≥ 12 years with at least 150 previous EDs to a FVIII concentrate will be enrolled by up to 15 study sites in the US and Europe to obtain evaluable data on 50 patients who complete 6 months of prophylactic treatment. Of these 50 patients, 20 patients will undergo two 2-day PK Assessment Phases of 1 dose of $50 \text{ IU} \pm 5 \text{ IU}$ *Wilate*/kg BW each before the start and after the end of the Prophylactic Treatment Phase. Of the 20 patients undergoing PK assessment, a minimum of 4 patients should be between ≥ 12 and < 17 years of age. The study is scheduled to start in the 4th quarter of 2016 and to be completed in the 4th quarter of 2017. The planned duration for an individual patient is 6 months (+2 weeks) and at least 50 EDs, plus a Follow-up Contact 30 days after the Completion Visit. For the 20 patients undergoing PK assessment, the study duration extends over an additional about 4 days.

The primary objective of this study is to determine the efficacy of *Wilate* in the prophylactic treatment of previously treated patients (PTP) with severe hemophilia A. Secondary objectives of this study include the FVIII:C PK profile of *Wilate*, its efficacy in the treatment of breakthrough BEs as well as the product's safety and tolerability. An additional objective is the descriptive efficacy of *Wilate* in surgical prophylaxis.

3.3 Discussion of Study Design

This prospective, international, multi-center phase 3 study was designed in accordance with the Guideline on the clinical investigation of recombinant and human plasma-derived factor VIII products (EMA/CHMP/BPWP/144533/2009).

The primary endpoint of this study is a 50% reduction of the total annualized bleeding rate (TABR) observed in the GENA-01 study, with a total of 58.1 BEs per patient per year. Comparison of the TABR in a prophylactic *Wilate* treatment setting with the average TABR reported in another study in severe hemophilia A in an on-demand setting is considered relevant to support the efficacy claim of *Wilate* treatment.

The bleeding rate observed in GENA-01 was selected as a basis for comparison in this study because this approach has previously been agreed on with FDA in the context of prophylactic studies with Octapharma's recombinant human cell line derived FVIII product *Nuwiq*[®].

Historical data on ABRs from clinical studies with *Wilate* in which patients received on-demand treatment only are not available. Therefore, we chose to compare the TABR seen in a previous prospective clinical study with *Nuwiq* obtained in a patient population expected to be similar to the population that will be included in WIL-27.

GENA-01 was a prospective, randomized, actively controlled (for PK assessment), open-label, cross-over, multi-center phase II study of the PK, efficacy, safety, and immunogenicity *Nuwiq* in PTPs with severe hemophilia A. The study, which included a total of 22 PTPs aged between 12 and 65 years, evaluated the PK of *Nuwiq* and the efficacy and safety of on-demand home treatment with *Nuwiq* for at least 6 months and at least 50 EDs as well as use of the product in surgical prophylaxis.

4 STUDY POPULATION

4.1 Population Base

Overall, 55 patients aged ≥ 12 years will be enrolled into the study, with the aim to obtain data on 50 patients who complete the 6-month Prophylactic Treatment Phase.

A total of 20 patients will undergo two 2-day PK Assessment Phases of 1 dose of *Wilate* each before the start and after the end of the Prophylactic Treatment Phase. Of the 20 patients undergoing the PK assessment, a minimum of 4 patients should be between ≥ 12 and < 17 years of age.

4.1.1 Inclusion Criteria

Patients who meet all of the following criteria are eligible for the study:

1. Severe hemophilia A ($< 1\%$ FVIII:C) according to medical history
2. Male patients aged ≥ 12 years
3. Previous treatment with a FVIII concentrate for at least 150 exposure days (EDs)
4. Immunocompetence (CD4+ count $> 200/\mu\text{L}$)
5. Good documentation of the historical bleeding rate (at least for the 6 months preceding study start)
6. Voluntarily given, fully informed written and signed consent obtained by the patient (or parent/legal guardian in case of adolescents) before any study-related procedures are conducted

Whenever possible, the interval between the Screening Visit and the PK or Non-PK Visit **should not exceed 30 days**. If the 30-day interval is exceeded, determination of the CD4+ count is to be repeated and must be $> 200/\mu\text{L}$ for patients to be enrolled (i.e., exclusion criterion no. 4).

4.1.2 Exclusion Criteria

Patients who meet any of the following criteria are *not* eligible for the study:

1. Any coagulation disorders other than hemophilia A
2. History of FVIII inhibitor activity (≥ 0.6 BU) or detectable FVIII inhibitory antibodies (≥ 0.6 BU using the Nijmegen modification of the Bethesda assay) at screening, as determined by the central laboratory
3. Severe liver or kidney diseases (alanine aminotransferase [ALAT] and aspartate transaminase [ASAT] levels > 5 times of upper limit of normal, creatinine $> 120 \mu\text{mol/L}$)
4. Patients receiving or scheduled to receive immunomodulating drugs (other than anti-retroviral chemotherapy) such as alpha-interferon, prednisone (equivalent to > 10 mg/day), or similar drugs
5. Treatment with any investigational medicinal product in another interventional clinical study currently or within 4 weeks before enrollment

4.2 Prior and Concomitant Therapy

To be enrolled in this study, patients have to have had at least 150 previous EDs to a FVIII concentrate. Patients receiving or scheduled to receive immunomodulating drugs (other than anti-retroviral chemotherapy) such as alpha-interferon, prednisone (equivalent to >10 mg/day), or similar drugs may not be enrolled.

Other than that, concomitant therapies not interfering with the objectives of the study are permitted. Details of any concomitant medications must be recorded in the electronic Case Report Form (eCRF).

4.3 Withdrawal and Replacement of Patients

4.3.1 Premature Patient Withdrawal

Patients have the right to withdraw from the study at any time for any reason, without the need to justify their decision. The Investigator also has the right to withdraw patients in case of AEs, poor compliance, or other reasons. Since an excessive rate of withdrawals can render the study noninterpretable, any unnecessary withdrawal of patients should be avoided.

For any withdrawals after study entry, the Investigator will obtain all the required details and document the reason(s) for discontinuation. If the reason for withdrawal of a patient is an AE, the main specific event or laboratory test will be recorded, and the Investigator will make thorough efforts to clearly document the outcome.

4.3.2 Patient Replacement Policy

Patients withdrawn from the study for safety reasons will not be replaced.

4.4 Assignment of Patients to Treatment

The Investigator will enter a unique identifier of each patient in both the eCRF and the confidential patient identification list and inform the monitor of new patients enrolled.

Overall, 20 patients will undergo PK assessment with *Wilate*, followed by prophylactic treatment with *Wilate* for 6 months and a second PK assessment at the Study Completion Visit. Of these 20 patients, a minimum of 4 patients should be between ≥ 12 and < 17 years of age.

The remaining patients will start the study with prophylactic treatment with *Wilate*, with the first prophylactic treatment including an IVR assessment.

Patients who enroll in the study will not be permitted to re-enroll.

4.5 Relevant Protocol Deviations

In case of any major protocol deviation, the Investigator and Octapharma will decide on the further participation of the patient in this study after having discussed all relevant aspects.

5 INVESTIGATIONAL MEDICINAL PRODUCT

5.1 Characterization of *Wilate*

Wilate, produced from the plasma of human donors, is presented as a powder and solvent for intravenous injection containing nominally 500 IU/1000 IU human von Willebrand factor (VWF) and human FVIII per vial. The ratio between von Willebrand factor ristocetin cofactor activity (VWF:RCo) and FVIII:C is 1:1.

The product contains approximately 100 IU/mL human coagulation factor VIII when reconstituted with 5 mL/10 mL water for injections with 0.1% Polysorbate 80. The FVIII potency (IU) is determined using the European Pharmacopoeia chromogenic assay. The injection or infusion rate should be 2–3 mL per minute.

5.2 Packaging and Labelling

Final labelling will comply with the national requirements of each country where the study is conducted.

5.3 Conditions for Storage and Use

The powder and solvent vials must be stored in a refrigerator (2–8°C). The vials must be kept in the outer carton to protect from light and must not be frozen.

The product can be stored at room temperature (max. 25°C) for 2 months. In this case, the shelf-life expires 2 months after the product has been taken out of the refrigerator for the first time.

The Investigator and any authorized personnel at the site will ensure that the IMP is stored in appropriate conditions with restricted access and in compliance with national regulations.

5.4 Dose and Dosing Schedule

5.4.1 PK Assessment Phases

In the 2 PK Assessment Phases performed in a subset of 20 patients before the start and after the end of the Prophylactic Treatment Phase, *Wilate* will be administered to all 20 patients as a single dose of 50 ± 5 IU/kg BW. Full vials should be used. The dose can be rounded to the next higher or lower full vial.

5.4.2 Prophylactic Treatment Phase

In the Prophylactic Treatment Phase, *Wilate* should be administered every 2 to 3 days at a dose of 20–40 IU/kg BW for 6 months (+2 weeks) and at least 50 EDs.

In case of unacceptably frequent spontaneous breakthrough BEs (i.e., more than 2 spontaneous BEs or 1 major or life-threatening spontaneous BE within a 30-day period), the dose of *Wilate* should be increased by approximately 5 IU/kg (depending on the entire content of the additional vial(s) that need(s) to be reconstituted).

5.4.3 Treatment of Breakthrough BEs

The dose (and duration) of treatment of BEs will depend on the location and extent of bleeding and on the clinical condition of the patient. The dose calculation is based on the empirical finding that 1 IU FVIII:C/kg BW raises the plasma level by 1.5–2.0% of normal activity. The recommended dose is determined using the following formula:

$$\text{Recommended units} = \text{body weight (kg)} \times \text{desired factor VIII rise (\%)} \text{ (IU/dL)} \times 0.5$$

In the case of the following hemorrhagic events, the factor VIII activity should not fall below the given plasma FVIII activity level (%) in the corresponding period. The following can be used to guide dosing in BEs:

- **Early hemarthrosis, muscle bleeding, or oral bleeding**
Target FVIII level: 20–40%
Recommended dose: 10–20 IU/kg
Repeat injection every 12–24 hours. At least 1 day, until the BE as indicated by pain has resolved or healing has been achieved.
- **More extensive hemarthrosis, muscle bleeding, or hematoma**
Target FVIII level: 30–60%
Recommended dose: 15–30 IU/kg
Repeat injection every 12–24 hours for 3 to 4 days or more until pain and disability have resolved.
- **Life-threatening hemorrhages**
Target FVIII level: 60–100%
Recommended dose: 30–50 IU/kg
Repeat injection every 8–24 hours until threat has resolved.

5.4.4 Surgical Prophylaxis

- **Minor surgeries, including tooth extractions**
Target FVIII level: 30–60%
Recommended dose: 15–30 IU/kg
Every 24 hours, at least 1 day, until healing is achieved.
- **Major surgeries**
Target FVIII level: 80–100% (pre- and postoperative)
Recommended dose: 40–50 IU/kg
Repeat injection every 8–24 hours until adequate wound healing, then therapy for at least another 7 days to maintain a FVIII activity of 30% to 60%.

During treatment, appropriate determination of FVIII:C levels is advised to guide the dose to be administered and the frequency of repeated infusions. In the case of major surgical interventions in particular, precise monitoring of the substitution therapy by means of coagulation analysis (FVIII:C) is indispensable. Individual patients may vary in their response to FVIII treatment, achieving different half-lives and recoveries.

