7.2.4 Surgical Prophylaxis Data

The following surgery-related parameters will be documented:

- Body weight within 12 hours before the start of surgery
- Safety laboratory tests (hematology, chemistry) within 12 hours before the start of surgery and 24 hours after the end of surgery (see **Section 7.3.5.2**)
- Vital signs within 12 hours before the start of surgery (before blood sampling)
- Type of surgery (planned or emergency)
- Location of surgery
- Severity of surgery (minor, major) (see definitions under **(a)** below)
- Expected duration of surgery
- Actual duration of surgery (start and end times, i.e., skin to skin)
- Details on IMP dose(s) given pre-, intra-, or postoperatively (see **Section 7.2.1**)
- Pre-, intra-, and postoperative FVIII plasma levels (see definitions under **(b)** below)
- Expected and actual blood loss (see item **(d)** below)
- Presence of wound hematomas and whether or not they require surgical evacuation
- Efficacy assessments at the end of surgery by surgeon (see **Section 7.2.5.1**)
- Efficacy assessment at the end of the postoperative period by hematologist (see **Section 7.2.5.2**)
- Overall efficacy assessment by the Investigator (see **Section 7.2.5.3**)

- Narrative describing the outcome and efficacy of the intervention
- Monitoring of AEs
- Details on concomitantly administered products, including any blood or blood product transfusions but excluding drugs given for routine anesthesia
- Inhibitor testing (see **Section 7.3.5.2**), with a plasma sample obtained within 3–8 weeks after the end of the surgery; this visit can coincide with another study visit with scheduled inhibitor testing.

(a) Severity of surgery

Surgeries are defined as **major** if any of the following criteria are met:

- General or spinal anesthesia required
- Opening into the great body cavities required
- Hemostatic therapy for at least 6 days required
- Orthopedic interventions involving joints (ankle, knee, hip, wrist, elbow, shoulder)
- 3rd molar extraction or extraction of ≥ 3 teeth
- Surgeries/conditions in which the patient's life is at stake

The classification is made prospectively. All other surgeries are classified as **minor**.

(b) Definitions of periods and time points before, during, and after surgery

- **Preoperative** is defined as the time period of up to 3 hours before the start of surgery.
- The **end of surgery** is defined as the time immediately after the last surgical suture.

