5.9 Surgeries

Efficacy in surgical prophylaxis will be analyzed descriptively, presenting summary tables and listing on all aspects of surgical treatment and procedures as well as efficacy ratings.

The following surgery-related parameters will be presented:

- Number of minor and major surgeries

STATISTICAL ANALYSIS PLAN

Protocol No: WIL-27

Version Number: 5.0

Date of Issue: 2018-05-08

Page 22 of 27

- Location, severity (minor or major, for definitions see protocol), and type (planned or emergency) of surgery
- Expected and actual duration of surgical procedure
- Expected and actual blood loss
- Pre-, intra-, and/or postoperative IMP administration data (only listed)
- Pre-, intra-, and postoperative FVIII plasma levels (only listed)
- VWF:Ag and VWF:Ac (descriptive statistics including changes to pre-infusion)
- Presence of wound hematomas and whether or not they require surgical evacuation (only listed)
- Assessment of efficacy of surgical prophylaxis:
 1. at the end of surgery by the surgeon
 2. at end of the postoperative period by the hematologist
 3. Overall efficacy taking both the intra- and postoperative assessments into account assessed by the Investigator.
- Number of successively treated surgeries ('excellent' or 'good' overall efficacy rating)
- Concomitantly administered products (only listed)
- Narrative describing the outcome and efficacy of the intervention (only listed)
- Inhibitor testing (within 3–8 weeks after the end of the surgery, this visit may coincide with another study visit with scheduled inhibitor testing)

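### Protocol 7.2.4(a) classes third-molar and ≥3-tooth extractions as major surgery, but the minor dosing row in 5.4.4 names tooth extractions, so their dosing row is ambiguous

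*Protocol*

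**What the plan says.** **Dosing.** Protocol 5.4.4 gives two rows, repeated in the Study Outline.

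- The first is headed "Minor surgeries, including tooth extractions". It gives an FVIII target of 30–60%, "Recommended dose: 15–30 IU/kg", and the schedule "Every 24 hours, at least 1 day, until healing is achieved".
- The second is for major surgery. It gives a target of 80–100% before and after the operation and "Recommended dose: 40–50 IU/kg", repeated every 8–24 hours until the wound has healed adequately. Therapy then continues for at least 7 more days to hold FVIII at 30–60%.

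**Severity.** Protocol 7.2.4(a) makes a surgery major if it meets any one of six criteria, and minor otherwise. The class is assigned prospectively. One criterion is "3rd molar extraction or extraction of ≥ 3 teeth".

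**Consequences of the class.** Protocol 7.2.4(c) makes FVIII levels mandatory for the first 3 postoperative doses when surgery is major. SAP 5.9 reports "Number of minor and major surgeries" and refers to the protocol for the definitions. It also presents severity and the efficacy ratings, and lists the doses given and the FVIII levels.

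**The concern.** The dosing section names tooth extractions under minor surgery, and the severity definition puts some of them under major. Section 5.4.4 does not mention 7.2.4(a), and nothing in its heading signals that certain extractions belong in the other row. A site that plans a wisdom-tooth extraction from the dosing section or the Study Outline would reach one regimen. A site that classifies the procedure first would reach the other. Both could say that they followed the protocol.

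What is at stake is a dosing instruction in patients with FVIII below 1%. Section 1.1 itself cites tooth extraction as a small intervention after which serious bleeding can occur. For the analysis, a procedure recorded as major may have been managed on the minor regimen, and an efficacy summary of major surgery would then include it.

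**Working it through.** **1. Are the two rows internally consistent?** Protocol 5.4.3 converts a desired FVIII rise to a dose: IU/kg = rise (%) × 0.5. The formula is given there for bleeding episodes. Applied to the surgical targets:

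- Minor: 30 × 0.5 = 15 and 60 × 0.5 = 30, so 15–30 IU/kg, as stated.
- Major: 80 × 0.5 = 40 and 100 × 0.5 = 50, so 40–50 IU/kg, as stated.

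Each row agrees with its own target. The difficulty is only which row applies.

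**2. Do the rows overlap before wound healing?**

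- Dose: the minor row ends at 30 and the major row starts at 40 IU/kg, a gap of 10 IU/kg.
- Target: the minor row ends at 60% and the major row starts at 80%, a gap of 20 percentage points.
- Per-dose ratio, major to minor: smallest 40/30 = 1.33, largest 50/15 = 3.33.

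No recommended dose satisfies both rows. Body weight is not given in the documents. For assumed weights:

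| Assumed weight | Minor row, IU per dose | Major row, IU per dose |
|---|---|---|
| 40 kg | 600–1200 | 1600–2000 |
| 70 kg | 1050–2100 | 2800–3500 |
| 100 kg | 1500–3000 | 4000–5000 |

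**3. And after wound healing?** The major row's continuation phase aims at 30–60%, the same range as the minor row. The targets therefore differ only until healing. The major row then adds at least 7 days of therapy, whereas the minor row ends at healing.

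**4. Which extractions are affected?**

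| Extraction | Row that names it in 5.4.4 | Class under 7.2.4(a) |
|---|---|---|
| 1–2 teeth, no third molar, no other major criterion | Minor | Minor |
| Third molar | Minor | Major |
| 3 or more teeth | Minor | Major |

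Only the last two lines disagree.

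**5. What else depends on the class?** The mandatory postoperative sampling stands in the same Section 7.2.4 as the definition, so major there means major under 7.2.4(a). SAP 5.9 points to the protocol's definitions, and 7.2.4(a) is the only one. Sampling and counts are therefore determined. Only the dosing row is not.

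**The case against.** The best defence is that the sections can be read in sequence. Section 7.2.4(a) is the only definition of severity and is applied before the operation, while 5.4.4 merely gives doses by class. On that reading the words about tooth extractions cover only those left as minor after classification, and there is no conflict. This reading is possible, and it is why the point is one of ambiguity and not of outright contradiction. But the protocol does not state it. Section 7.2.4 is introduced as a list of items to document, not as a rule for choosing a dose, and Section 1.4 says that the perioperative doses are taken from the European product information. Nothing in 5.4.4 sends the reader to the severity list.

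Several stronger readings are tempting, and the documents do not support them:

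- **That the regimens differ throughout.** They share the 30–60% target once the wound has healed.
- **That the contrast is 1 day against more than 7 days.** The minor row also runs until healing, and no healing time is given, so total durations cannot be compared.
- **That the minor/major counts or the sampling rule are undefined.** Both follow from 7.2.4(a).
- **That small numbers of surgeries make the mixing worse.** Neither document forecasts how many surgeries, or how many such extractions, will occur.
- **That sites would in fact under- or over-treat.** The doses are recommendations, and 5.4.4 advises measuring FVIII:C to guide them.

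**Conclusion.** The point holds as an ambiguity confined to third-molar extractions and extractions of 3 or more teeth. For these, two non-overlapping dosing rows can each be read as applicable until wound healing, with a gap of 10 IU/kg and 20 percentage points of FVIII. A procedure classified, sampled and tabulated as major could be dosed by the minor row. Any SAP 5.9 efficacy summary of major surgery could then include procedures managed on the minor regimen. The mismatch would be visible in the listings of doses and FVIII levels, but not in the summary itself.

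A reader might infer that the trial's main conclusion is at risk. It is not: surgical efficacy is exploratory and descriptive, and surgery periods with their bleeds are left out of TABR (Protocol 3.1.1, SAP 5.7.1).

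The finding applies to protocol version 03 of 16-Jan-2017. SAP Section 1 cites a protocol dated 2017-09-07 that includes Amendment #04. Whether that text changed 5.4.4 or 7.2.4 cannot be seen from these documents.

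**What to change.** Reconcile Protocol 5.4.4 and the Study Outline with 7.2.4(a), so that each type of tooth extraction maps to exactly one severity class and one dosing row. A cross-reference from the dosing rows to the severity definition is one way to do it. Which class and row apply to third-molar and ≥3-tooth extractions is for the sponsor's clinical team to decide.

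The cost is one clarifying line in the protocol or in a letter to sites, with no new data or patients. If the later protocol version already contains that line, nothing further is needed. The SAP needs no additional listing column, because severity, doses and FVIII levels are already presented or listed under 5.9.
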